7.2.3 Serious Adverse Event

All SAEs, regardless of attribution, occurring from time of signed informed consent, through 100 days after the last administration of study drug, must be reported upon discovery or occurrence.

An SAE is defined in regulatory terminology as any untoward medical occurrence that:

- **Results in death.**

If death results from (progression of) the disease, the disease should be reported as event (SAE) itself.

- **Is life-threatening.**

The patient was at risk of death at the time of the event; it does not refer to an event that hypothetically might have caused death if it were more severe.

- **Requires in-patient hospitalization or prolongation of existing hospitalization for ≥ 24 hours.**

- **Results in persistent or significant disability or incapacity.**

- **Is a congenital anomaly/birth defect.**

- **Is an important medical event.**

Any event that does not meet the above criteria, but that in the judgment of the investigator jeopardizes the patient, may be considered for reporting as a serious adverse event. The event may require medical or surgical intervention to prevent one of the outcomes listed in the definition of "Serious Adverse Event".

For example: allergic bronchospasm requiring intensive treatment in an emergency room or at home; convulsions that may not result in hospitalization; development of drug abuse or drug dependency.

7.2.4 Unanticipated Problems Involving Risks to Subject or Others

A UPIRSO is a type of SAE that includes events that meet ALL of the following criteria:

- Is *unanticipated* in terms of nature, severity, or frequency
- Places the research subject or others at a different or *greater risk of harm*
- Is deemed to be *at least possibly related* to participation in the study.

7.2.5 Adverse Event Reporting Period

For this study, adverse events will be followed from the time of informed consent until 30 days following the last administration of study treatment. SAE's will also be collected from the time of consent until 100 days following the last administration of study treatment. For patients registered and never treated with study drug, SAE's should be collected for 30 days from the date of consent.

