2.2 Secondary Objectives & Endpoints

- 2.2.1** To evaluate the proportion of patients alive and progression free at 24 weeks in the described population.
- 2.2.2** To evaluate the toxicities (according to the NCCN CTCAE v4.03) and tolerability of nivolumab and y-90 in patients with advanced hepatocellular carcinoma
- 2.2.3** To determine the disease control rate (DCR) to the combination of nivolumab and Y-90 at 24 months from the start of nivolumab treatment. DCR is defined as the sum of Complete Response, Partial Response, and Stable Disease (DCR = CR + PR + SD).

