4.0 TREATMENT PLAN

4.1 Overview

Treatment will be administered on an outpatient basis. Patients will first be treated one time with liver directed therapy, Therasphere® (Y-90), following institutional procedures**. During screening, each patient will undergo an angiogram in interventional radiology to determine the appropriate Y-90 dose. Within 7-14 days, patients will begin treatment with intravenous nivolumab as maintenance either at 80mg (first 3 patients in Phase I) or 240mg (Phase Ib if MTD) over 30 minutes (-5 minutes / +15 minutes) every 2 weeks (Day 1 & 15 of each cycle; 1 cycle = 28 days).

After study registration, the patient will proceed to receiving Y-90 per the standard of care procedures listed in section 8.1. Y-90 administration is normally planned around 7 days from the angiogram, so registration should be planned accordingly. After completion of Y-90, patients will have 1-2 weeks recovery time prior to proceeding with nivolumab administration (4 weeks if necessary). This window allows for recovery from generalized fatigue. Study drug nivolumab will continue until disease progression or withdrawal of treatment by patient.

*** Repeat therapy to the treated lesion or additional untreated lesions may be warranted. If a patient requires additional Y-90 after starting nivolumab treatment, it may be given once approval from the interventional radiologist and treating physician has been confirmed. In such cases, nivolumab should be held for ≥ 7 days prior to administering Y-90. Nivolumab can be resumed at least 7 days after receiving additional Y-90, but can be delayed for up to 4 weeks if needed.*

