4.10 Patient Replacement

Any patient who signs consent but does not receive study treatment may be replaced. In addition, any study patient who receives Y-90 but discontinues prior to treatment with nivolumab can be replaced. This includes patients who cannot start nivolumab within 4 weeks of Y-90 treatment, who must come off study.

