5.0 STUDY PROCEDURES

	Screening ¹	On Treatment (1 cycle = 28 days)				Off Treatment		
Time Period	Baseline	Induction Treatment ⁹	Cycle 1 ¹⁰ (± 3 days)		Cycle 2+ (± 3 days)		End of Treatment ¹³	Follow-up ¹⁴
			D1	D15	D1	D15		
Assessment or Activity								
Informed Consent	X							
Medical history	X							
Physical exam ²	X		X		X			
ECOG status	X		X		X			
Adverse Events & ConMeds	X	X	X		X		X	X
Tumor Measurement ³	X		X ³		X ³			
Coagulation studies (INR, PT, PTT) ⁴	X ⁴							
Child-Pugh Class	X		X					
CBC with diff ⁵	X ⁵		X	X	X	X	X	
Chemistry panel ⁶	X ⁶		X	X	X	X	X	
AFP	X		X		X			
TSH with reflex T3, T4			X		X			
Hepatitis Panel ⁷	X						X	
Urinalysis	X						X	
Pregnancy Test ⁸	X	X	X				X	
ECG	X							
Angiogram ⁹	X							
Y-90 ⁹		X						
Nivolumab ¹⁰			X	X	X	X		
Correlative studies ¹¹	X		X		X ¹¹			
Archival tissue collection ¹²	X							
Survival status ¹⁴								X

1 All screening procedures should take place within 28 days of registration unless noted otherwise.

2 Includes vital signs (pulse, respirations, blood pressure), height (baseline only) and weight.

- 3 Imaging will be performed at screening, 21-28 days after Y-90 administration (during Cycle 1), and every 2 cycles (starting with Cycle 3 Day 1, ± 7 days) for the first 13 months. Imaging will then occur every 3 cycles (± 7 days) until disease progression or treatment discontinuation. Imaging will include either CT of Chest/Abdomen/Pelvis or MRI as indicated. Contrast should be used to the greatest extent possible (see section 6.1 for details).
- 4 Coagulation studies will be performed at the time of the screening angiogram. Patients who are on Coumadin will require their INR to be checked every cycle or according to the treating oncologist. If patient is on low molecular weight heparin, an Anti-Xa level should be tested to ensure it is within therapeutic range
- 5 CBC with differential will include WBC, ANC, ALC, Platelets, and Hemoglobin. CBC should be collected within 14 days prior to registration and reviewed prior to each nivolumab treatment.
- 6 Chemistry panel will be drawn at screening (within 14 days prior to registration) and pre-dose at all treatment visits. Chemistry panel will include glucose, calcium, albumin, ALT, AST, sodium, potassium, total bilirubin, alk phos, and creatinine.

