6.3 Secondary Endpoints

- For the purposes of this study, patients who have received at least one dose of nivolumab will be considered for evaluation of the safety and toxicity profile of the combination therapy. Safety and tolerability will be measured by the incidence of all adverse events, serious adverse events, deaths and laboratory abnormalities. Adverse event assessments and laboratory tests will be performed at baseline, and continuously throughout the study at the beginning of each subsequent cycle.
- All patients should be re-evaluated for response 21-28 days after Y-90 then every 8 weeks (every 12 weeks after 13 months) using RECIST criteria. Overall response will be calculated by sum of the complete and partial response rates according to measurement of target and non-target lesions as described below.
- Disease control rate will be determined at 24 months from the start of nivolumab treatment by the sum of complete response, partial response and stable response according to measurement of target and non-target lesions as described below.
- Patients who have a response sufficient enough where by shrinkage of the tumors allows them to be considered for transplant will be determined by established BCLC transplant guidelines for individual tumor sizes.
- PFS is defined as the duration of time from start of treatment to time of progression or death, whichever occurs first. Progression assessment will be performed by

investigator each time the patients has a radiologic evaluation after 8 weeks of treatment. OS is defined as the duration of time from start of treatment to time of death.

6.3.1 Definitions:

Evaluable for toxicity. All patients will be evaluable for toxicity from the time of their first treatment with nivolumab.

Evaluable for objective response. Only those patients who have measurable disease present at baseline, have received at least one dose of therapy, and have had their disease re-evaluated will be considered evaluable for response. These patients will have their response classified according to the definitions stated below. RECIST measurements should be used when available. When RECIST measurements cannot be made due to infiltrative disease, evaluable disease needs to be confirmed by pathology.

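### Read literally, the 30-days-from-consent SAE rule in 7.2.5 covers patients who receive Y-90 but never nivolumab, and can end their routine SAE collection shortly after Y-90 or even before it

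*Combined protocol and SAP*

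**What the plan says.** Section 7.2.5 sets two SAE windows. The general one is: "SAE's will also be collected from the time of consent until 100 days following the last administration of study treatment". The exception follows directly: "For patients registered and never treated with study drug, SAE's should be collected for 30 days from the date of consent". Section 7.2.3 counts the general window differently, "through 100 days after the last administration of study drug", and 4.8 also counts it from study drug.

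The terms are not defined. Section 4.1 ties study drug to nivolumab: "Study drug nivolumab will continue until disease progression or withdrawal of treatment by patient". Section 3.1.10 does the same by giving the study drug's five half-lives as 19 weeks. 'Study treatment' is equated with nivolumab in 4.7. In 4.10, however, patients who receive no study treatment are listed separately from those who receive Y-90 only, which suggests the term includes Y-90 there.

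Y-90-only patients are expected. Under 4.2.2 a patient who cannot start nivolumab within 28 days of Y-90 comes off study, and 4.10 says "any study patient who receives Y-90 but discontinues prior to treatment with nivolumab can be replaced".

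For analysis, 6.3.1 says "All patients will be evaluable for toxicity from the time of their first treatment with nivolumab", and 4.4 likewise requires a nivolumab dose. Secondary objective 2.2.2 is broader: "To evaluate the toxicities (according to the NCCN CTCAE v4.03) and tolerability of nivolumab and y-90 in patients with advanced hepatocellular carcinoma".

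**The concern.** Y-90 is half of the combination under study and is given after registration. A window that starts at consent and lasts 30 days takes no account of when, or whether, Y-90 was given. It suits a patient who was never treated at all. It does not suit one who has had radioembolization.

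The affected group is also selected. One route into it is toxicity after Y-90 that keeps the patient from starting nivolumab. The protocol itself treats Y-90 toxicity as material. Appendix 1 lists expected frequencies of 10% each for GI ulcer, ascites and elevated bilirubin, and 5% for renal failure. Section 8.1.9 refers to 12 deaths possibly related to the device in a 121-patient review. If these patients leave routine SAE collection early, are not evaluable for toxicity and are replaced, the summary for objective 2.2.2 leans towards patients who tolerated Y-90 well enough to go on.

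**Working it through.** The plan gives no figure for this, so the check is calendar arithmetic with consent as day 0.

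**Inputs**
- SAE window under the exception: closes on day 30 (7.2.5).
- Screening: "All screening procedures should take place within 28 days of registration unless noted otherwise" (5.0, footnote 1). Consent is a row in the screening column. I assume consent opens screening, so registration falls on day 28 at the latest.
- The planning angiogram precedes registration (5.0, footnote 9), so it falls on day a, from 0 to 28. Y-90 follows registration (4.1).
- Angiogram-to-Y-90 gap g: usually about 7 days (4.1), with a recommended maximum of 2–3 weeks (4.2.1). I use 7 to 21 days.
- Latest nivolumab start: 28 days after Y-90 (4.2.2).

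**Formulas**
- Y-90 day: y = a + g
- SAE cover after Y-90: 30 − y
- Nivolumab limit: y + 28

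| Angiogram day a | Gap g | Y-90 day y | Cover after Y-90 (30 − y) | Nivolumab limit (y + 28) |
|---|---|---|---|---|
| 0 | 7 | 7 | +23 | 35 |
| 7 | 7 | 14 | +16 | 42 |
| 21 | 7 | 28 | +2 | 56 |
| 23 | 7 | 30 | 0 | 58 |
| 28 | 7 | 35 | −5 | 63 |
| 28 | 21 | 49 | −19 | 77 |

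A negative value means that the window closed before Y-90 was given. This requires a + g > 30: an angiogram on day 24 or later with a 7-day gap, or on day 10 or later with a 21-day gap.

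The nivolumab limit runs from day 35 to day 77, so the window always closes first. It therefore ends before the patient can be finally classed as never treated.

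**Comparison.** Take Y-90 on day 14 and a single nivolumab dose 7 days later, on day 21. SAE collection then runs to day 21 + 100 = 121. The same patient without that dose is covered to day 30 under the exception.

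**The two sentences of 7.2.5 for a Y-90-only patient**
- If study treatment includes Y-90, the general sentence gives 100 days after Y-90 and the exception gives 30 days from consent. The two conflict.
- If study treatment means nivolumab, as in 4.7, the general sentence has no starting date for this patient. Only the exception applies.

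Neither reading gives a single clear window counted from Y-90.

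**The case against.** The strongest reply is that this is a problem of terms rather than a gap. On the broad meaning suggested by 4.10, the general sentence already gives Y-90-only patients 100 days, and an exception counted from consent makes most sense for a wholly untreated patient. That may well be the intent. But 4.7 supports the narrow meaning, and the exception is the more specific rule and is worded in terms of study drug. Staff applying it as written would stop at day 30.

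The second reply is that other clauses catch the events. Section 7.2.8 requires the investigator to notify the DSMC of later deaths or adverse events that may reasonably be related. Section 7.3.2 covers all events within 30 days of the last protocol treatment, and attributed events after that. This stands in part. A reader might infer that the DSMC would not see these patients' events, and the documents do not support that. But 7.2.8 and the later part of 7.3.2 depend on relatedness, and the 30-day part depends on whether the undefined 'protocol treatment' includes Y-90. Section 7.2.3 requires SAEs whatever their attribution.

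Third, a reader might infer that toxicity between Y-90 and nivolumab goes unrecorded. It does not. The 5.0 table collects adverse events at induction, 4.2.1 requires an evaluation within 14 days of Y-90, and 10.2 summarizes adverse events for all patients. For patients who go on to nivolumab, the problem is formal evaluability under 4.4 and 6.3.1. That sits awkwardly beside 2.2.2 and 10.2 but is not a failure of collection. Section 4.3.1 also counts a toxicity delay of more than 2 weeks in starting nivolumab as a DLT.

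**Conclusion.** The point holds as a defect of wording with a real consequence. Followed literally, 7.2.5 ends attribution-independent SAE collection for Y-90-only patients between 23 days after and 19 days before Y-90, and in every case before the deadline for starting nivolumab. The range rests on two assumptions: that consent opens a screening period of up to 28 days, and that the angiogram-to-Y-90 gap is 7 to 21 days. The documents do not state the actual consent-to-Y-90 interval. The negative values need late angiograms or long gaps and should not be taken as typical.

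A reader might go further and conclude that the reported toxicity is biased by a material amount. The documents give neither the expected number of Y-90-only patients nor their event rates. The direction is plausible, but the size is unknown. The 3+3 rules in 4.3 and the Simon design in 10.1 do not use this SAE window. The rule should still be corrected, because it can cut short safety capture after an on-study intervention whose toxicity is a stated objective.

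**What to change.** 1. Define 'study drug', 'study treatment' and 'protocol treatment' once, and reconcile 4.8, 7.2.3, 7.2.5 and 7.3.2 with those definitions.
2. In 7.2.5, restrict the 30-days-from-consent exception to registered patients who receive neither Y-90 nor nivolumab.
3. For patients who receive Y-90 only, count the protocol's existing windows, 100 days for SAEs and 30 days for AEs, from the last Y-90. With Y-90 on days 7 to 49, SAE collection would end on days 107 to 149 and AE collection on days 37 to 79.
4. In 4.4 and 6.3.1, start safety evaluability for the 2.2.2 toxicity summary at Y-90, in line with 10.2. Leave the DLT definition unchanged.

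The cost is an amendment to wording and some extra follow-up of what should be a few patients. The toxicity table may look slightly less favourable. The changes need no additional patients.

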7.2.6 Preexisting Condition

A preexisting condition is one that is present at the start of the study. A preexisting condition should be recorded as an adverse event if the frequency, intensity, or the character of the condition worsens during the study period.

7.2.7 General Physical Examination Findings

At screening, any clinically significant abnormality should be recorded as a preexisting condition. At the end of the study, any new clinically significant findings/abnormalities that meet the definition of an adverse event must also be recorded and documented as an adverse event.

7.2.8 Post-study Adverse Event

All unresolved adverse events should be followed by the investigator until the events are resolved, the subject is lost to follow-up, or the adverse event is otherwise explained. At the last scheduled visit, the investigator should instruct each subject to report any subsequent event(s) that the subject, or the subject's personal physician, believes might reasonably be related to participation in this study. The investigator should notify the DSMC of any death or adverse event occurring at any time after a subject has discontinued or terminated study participation that may reasonably be related to this study. The sponsor should also be notified if the investigator should become aware of the development of cancer or of a congenital anomaly in a subsequently conceived offspring of a subject that has participated in this study.

7.2.9 Abnormal Laboratory Values

All clinical laboratory abnormalities should be documented as adverse events.

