7.2 Definitions & Descriptions

7.2.1 Adverse Event

An **adverse event** (AE) is any symptom, sign, illness or experience that develops or worsens in severity during the course of the study. Intercurrent illnesses or injuries should be regarded as adverse events. Abnormal results of diagnostic procedures are considered to be adverse events if the abnormality:

- results in study withdrawal
- is associated with a serious adverse event
- is associated with clinical signs or symptoms
- leads to additional treatment or to further diagnostic tests
- is considered by the investigator to be of clinical significance

Recording of AEs should be done in a concise manner using standard, acceptable medical terms. In general, AEs are not procedures or measurements, but should reflect the reason for the procedure or the diagnosis based on the abnormal measurement. Preexisting conditions that worsen in severity or frequency during the study should also be recorded (a preexisting condition that does not worsen is not an AE). Further, a procedure or surgery is not an AE; rather, the event leading to the procedure or surgery is considered an AE.

If a specific medical diagnosis has been made, that diagnosis or syndrome should be recorded as the AE whenever possible. However, a complete description of the signs, symptoms and investigations which led to the diagnosis should be provided. For example, if clinically significant elevations of liver function tests are known to be secondary to hepatitis, "hepatitis" and not "elevated liver function tests" should be recorded. If the cause is not known, the abnormal test or finding should be recorded as an AE, using appropriate medical terminology (e/g/ thrombocytopenia, peripheral edema, QT prolongation).

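### Sections 7.2.1, 7.2.6 and 7.2.9 give different rules for when a laboratory abnormality is an adverse event, so the reported incidence of laboratory adverse events depends on which section is followed

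*Combined protocol and SAP*

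**What the plan says.** Section 7.2.9 consists of one sentence: "All clinical laboratory abnormalities should be documented as adverse events".

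Section 7.2.1 defines an AE more narrowly, as something that "is any symptom, sign, illness or experience that develops or worsens in severity during the course of the study". It adds a filter for test results: "Abnormal results of diagnostic procedures are considered to be adverse events if the abnormality" meets one of five conditions. These are study withdrawal, association with a serious AE, association with signs or symptoms, further treatment or testing, or clinical significance in the investigator's view. The same section says that "a preexisting condition that does not worsen is not an AE". Its example ("if clinically significant elevations of liver function tests are known to be secondary to hepatitis") shows that it has laboratory tests in mind.

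Section 7.2.6 repeats the worsening requirement: "A preexisting condition should be recorded as an adverse event if the frequency, intensity, or the character of the condition worsens during the study period".

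These definitions feed secondary objective 2.2.2, "To evaluate the toxicities (according to the NCCN CTCAE v4.03) and tolerability of nivolumab and y-90". Section 6.3 makes that objective operational: "Safety and tolerability will be measured by the incidence of all adverse events, serious adverse events, deaths and laboratory abnormalities". Section 10.2 summarizes AEs descriptively and does not say which laboratory values count.

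**The concern.** Two people recording the same chemistry panel could reach different AE counts, each following a current section of the protocol. In this population that matters. Section 3.1.9 admits patients with AST and ALT up to 5 x ULN, bilirubin up to 3 x ULN, platelets from 50 x 10⁹/L and hemoglobin from 8.5 g/dL. Section 7.2.5 starts AE collection at consent, before Y-90. Section 5.0 schedules a blood count and a chemistry panel at every nivolumab visit. Abnormal values will therefore be frequent, and some will predate treatment.

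The trial has a single arm, so no control group carries the same background for comparison. At stake is the meaning of the laboratory part of the safety summary, which readers will take as a description of the combination's toxicity.

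**Working it through.** The documents state no AE rate, so there is no figure to reproduce. The check is mainly a comparison of texts.

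**Step 1. Three readings of the current text.**
- A: 7.2.9 taken literally. Every laboratory abnormality is an AE.
- B: 7.2.9 read within the general definition in 7.2.1. The five-condition filter is lifted for laboratory values, but the value must still be new or worse.
- C: 7.2.1 with its five conditions, plus 7.2.6.

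**Step 2. Hypothetical findings under each reading.**

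| Finding | A | B | C |
|---|---|---|---|
| AST raised at entry within the 5 x ULN limit, unchanged on study | AE | not an AE | not an AE |
| New low-grade ALT rise, no symptoms, no action, not judged significant | AE | AE | no listed condition met |
| New platelet fall leading to further tests | AE | AE | AE |
| Enzyme rise explained by diagnosed hepatitis | laboratory values recorded | laboratory values recorded | hepatitis recorded instead |

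The readings agree on the third row and differ on the others. The second row is uncertain even within C, because 7.2.1 also tells the recorder to enter an abnormal test as an AE when its cause is unknown.

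**Step 3. Does another section settle it?** Section 7.1 follows AEs until abnormal laboratory values return to baseline, which presupposes a change from baseline but states no recording rule. Section 6.3 lists laboratory abnormalities beside AEs as a separate safety measure, without defining either. Appendix 5 records that Amendment 2 removed conditions from 7.2.9 to match institutional policy. That explains the origin of the sentence, but no current section states an order of precedence.

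**Step 4. Possible size for one term.** Inputs:
- q = 0.75, the expected frequency of elevated SGOT after Y-90 (Appendix 1). SGPT and alkaline phosphatase have the same figure. It is a device figure, used here only for scale.
- N = 40, the target accrual (10.1), as the upper bound on the safety population.
- f, the share of these abnormalities that count under reading C. The documents give no value, so it runs over its full range from 0 to 1.

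The rate under 7.2.9 is q = 75%, or 0.75 × 40 = 30 patients. The rate under 7.2.1 and 7.2.6 is q × f. The gap is q × (1 − f).

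| f (assumed) | Rate under 7.2.1/7.2.6 | Patients of 40 | Gap (points) |
|---|---|---|---|
| 0 | 0% | 0 | 75 |
| 0.25 | 18.75% | 7.5 | 56.25 |
| 0.5 | 37.5% | 15 | 37.5 |
| 1 | 75% | 30 | 0 |

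Under reading A, unchanged entry abnormalities would add to the 7.2.9 count only. The documents give no frequency for them.

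**The case against.** The best defense is that the text can be harmonized. Section 7.2.9 is specific and was amended on purpose, so it naturally governs laboratory values, while the general definition in 7.2.1 still requires something to develop or worsen. That is reading B. It is sensible, but the protocol does not state it, and 7.2.1 and 7.2.6 carry no cross-reference to 7.2.9.

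The defense also limits what can be claimed. A reader might infer any of the following, and the documents do not support them:

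- **That unchanged cirrhosis-related values definitely become AEs of the combination, push the overall AE rate towards 100% and dilute true hepatic toxicity.** Section 7.2.9 does not say that unchanged values are AEs. This is only reading A.
- **That 7.2.1 discards many new enzyme rises.** The hepatitis example is a naming rule. The five conditions are broad, and abnormal tests of unknown cause are to be recorded.
- **That the safety results cannot be interpreted.** Section 10.2 summarizes AEs by type, severity, timing and attribution, among other features, so laboratory, low-grade and pre-treatment entries can be told apart. Section 6.3 also names laboratory abnormalities as their own measure.
- **That a narrow gap can be computed for 29 patients.** The 29 are the Phase Ib response sample. Toxicity is evaluable in everyone given nivolumab (4.4 and 6.3.1). Any single value of f is an assumption.

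What remains is the missing rule for laboratory values and for unchanged baseline findings, and the absence of a counting rule in 10.2.

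**Conclusion.** The inconsistency is real and lies between current sections. The reported incidence of laboratory AEs depends on which section is followed. The size cannot be estimated from the documents: for a term with 75% expected frequency the difference could be anything from 0 to 75 points, given the Appendix 1 figure and an unknown f.

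The link to objective 2.2.2 runs through section 6.3, because the objective itself names toxicity and tolerability and not an AE rate. Section 7.2.6 speaks of preexisting conditions and not of laboratory values by name, so it bears on abnormalities present at entry.

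The effect falls mainly on low-grade, asymptomatic laboratory terms in a descriptive summary. The DLT and MTD rules in 4.3 and 4.3.1 use their own grade and duration criteria, and the Simon design in 10.1 uses tumor response. Neither is affected. The point merits correction because the repair is cheap and changes a number that will be reported.

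**What to change.** Keep 7.2.9 as the data-capture rule, which preserves the institutional policy of recording every laboratory abnormality, and cross-refer 7.2.1 and 7.2.6 to it.

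In 10.2, state that reported AE incidence counts a laboratory abnormality only if it is new or at least one CTCAE v4.03 grade worse than the pre-Y-90 baseline. The denominator is all patients evaluable for toxicity. Add a separate table of shifts from baseline grade for the laboratory parameters, so that abnormalities present at entry stay visible without entering the AE incidence.

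The cost is a few lines of text and a little extra analysis work. Section 5.0 already collects blood counts and chemistry at screening and before each nivolumab dose. No new data collection is needed, and AEs already recorded under 7.2.9 need not be re-recorded, because the filter is applied at analysis.
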